Observations will be conducted over approximately 2-3 days per facility and will be scheduled to occur on different days of the week and at different times of the day to better reflect the timing and variation of services and practices affecting NCD care and HIV/NCD integration. Structured observations will incorporate time spent in facility departments that affect patient and NPHW flow for management of NCDs in PLHIV, particularly the ART clinic, the Outpatient Department (OPD), the laboratory, and pharmacy. The study observer(s) will introduce themselves to all HCWs and staff, accompanied by the facility in-charge, in a general round of introductions at the beginning of the observation-period, and subsequently sit in a single space (as much as possible) in departments of interest, making shorthand notes related to their observations of health facility operations, healthcare worker interactions, patientprovider interactions and informal conversations. Notes will be structured under general thematic headings, including environment and workflow for NCD care, NCD patient care services, Equipment and Lab services, Medications, HCW work patterns & behaviours, with a particular focus on NPHWs, and communication and rapport-building patterns, among others. Short hand notes will be recorded on sub-thematic areas, including the following: operations; equipment and medication availability; waiting times; record keeping; communication patterns; referral systems; and interactions among healthcare workers and patients. Notes will be expanded in full at the end of the day (or as soon as possible thereafter), and formalized into a summary memo, which will be stored in an electronic log for later analysis. No personal identifying information such as names will be documented in notes or reports to protect confidentiality of staff and patients.

TASKPEN Study

ii. Preparation of data collection tools (Non-human subjects research)

Piloting of WHOQOL-HIV Brief

WHOQOL-HIV BREF is an essential tool to assess quality of life, considered the '4th' 95-95-95 HIV indicator (i.e., beyond viral suppression), which will be a secondary outcome for the pilot and the later follow-on trial. As such, under this sub-aim, we will use the WHOQOL-HIV instrument previously adapted to the Zambian context, and pilot the WHOQOL-HIV BREF items focusing on ensuring semantic equivalence and assessing known group validity.

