Evaluation activities will be conducted in 2 high-volume, ACHIEVE-supported facilities and their surrounding catchment areas, henceforth referred to as the "pilot study sites" in Lusaka Province. These sites will be selected from among the 4 sites undergoing in-depth formative assessment under Objective #1. Tentatively, the pilot sites will be Chilenje 1st level hospital and George urban health centre, subject to approval by our TAC and findings from our formative assessment. The "mini" stepped wedge pilot will include all HIV-infected adults aged 18 years and older seeking care at the two pilot sites. Inclusion in the nested cohort will require documented HIV infection, age ≥ 18 years and one or more cardio-metabolic conditions or risk factors of interest described below (i.e., hypertension, diabetes/ pre-diabetes, and/or dyslipidaemia).

d. Selection of participants, sampling methods, sample size, enrolment and follow-up procedures

TASKPEN Study v1.3 13 December 2021 Page | 26

i. Description and source of population and catchment area

Based on existing PLHIV volumes at high-volume ACHIEVE supported sites in Lusaka, we expect to survey at least ~188 PLHIV meeting patient survey eligibility criteria at each site at baseline, midline, and endline (i.e., ~564 at each site or ~1128 participants in total) and to recruit approximately 100 baseline survey participants into the nested cohort at each site (i.e., ~200 total). For outcome ascertainment in the surveys, we will check vital signs, anthropomorphic measurements, and biomarkers. For outcome ascertainment in the nested cohort, we will review SmartCare, LIMS, and other MOH and CIDRZ registers and augment the abstraction of these routine data with study-driven primary data collection. Study-driven primary data collection in the nested cohort will include administration of the adapted WHOQOL-HIV-BREF-Zam and discrete choice experiment (DCE) questionnaire to these ~200 participants.

For the implementation outcome evaluation, we will conduct: 1) In-Depth Interviews (IDIs) with patients; 2) Focus Group Discussions (FGDs) with NPHWs and community health workers participating in the delivery of the TASKPEN; and 3) Key Informant Interviews (KII) with key stakeholders, such as policy makers from the Ministry of Health (MOH) and Clinic In-Charges, critical to implementation of the TASKPEN intervention. A brief implementation survey will be conducted with FGD participants at the end of each FGD.

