For nested cohort participants, study staff will ask them to provide locator information and to complete the midline and endline surveys (shortly after their routine HIV care visits) as part of their ~4 scheduled study follow up visits. Similar handling of abnormal vitals signs and lab testing values will be offered to nested cohort participants as patient survey participants. In addition, we will administer the brief

WHOQOL-HIV-BREF-Zam instrument and the discrete choice experiment questionnaire one time each during one of their ~4 follow up visits. Cohort enrolment will stop when the target number is reached. Finally, we will review cohort participants' HIV and NCD clinical data using a minimally sufficient set of identifying variables (i.e. first name, surname, date of birth, and SmartCare ART number) to follow them longitudinally in the routine medical record. To this end, we will abstract data from existing paper-based patient charts and MOH registers, as well as the electronic SmartCare EMR and LMIS systems to: 1) assess HIV and NCD outcomes (e.g., viral load); 2) evaluate WHO PEN outcome indicators of interest (e.g. proportion of PLHIV routinely screened for hypertension); and 3) monitor for efficient collection of routine data, including routine laboratory test results (e.g. viral load).

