For nested cohort participants, we will supplement the aforementioned routinely collected data with study-specific data collected through survey and CRF administration to assess medication adherence, quality of life, nutritional status, tobacco and alcohol use, and other NCD-related health parameters. The WHOQOL-HIV-BREF-Zam (Appendix G) will be administered in Nyanja or Bemba to nested cohort participants at our pilot sites to investigate the ability of the instrument items to discriminate between those with and without active symptoms related to HIV and co-morbid NCDs, as determined by differences in mean scores. A p-value less than 0.05 will be considered significant; items with non-significant differences between the two groups may be removed from a future iteration of the instrument.

All DCE questionnaires will be conducted one-on-one in private by a trained interviewer with consenting patient and provider participants. Each DCE will be explained verbally to participants. Each questionnaire is expected to last approximately 30 minutes. Before the DCE, the interviewer will conduct a brief review of each participant's clinic file to confirm HIV status, ART regimen, most recent CD4 cell count, most recent viral load, and cardio-metabolic conditions. The DCE questionnaire will be developed in English and translated into Bemba and Nyanja and then translated back to English to

validate the translation. The DCE questionnaire will be administered using the secure REDCap Mobile App on Android tablets, which can be used offline, and later uploaded to a secure database. The DCE starts with a simple vision and literacy test to ensure internal validity and facilitate quality control as sight is necessary for full comprehension of DCE choice tasks. The DCE then proceeds to provide an introduction of each attribute and its levels. Participants will be asked to rank the levels of each attribute based on their individual preferences. Each participant will receive 8-10 choice tasks on the tablet, and will be asked to choose between three hypothetical HIV/NCD integrated service delivery programs/ scenarios with different levels of attributes per choice task.

iv. Qualitative and mixed methods data collection

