IDIs, KIIs, and FGDs will be tape-recorded with participant permission for subsequent transcription. An interviewer/ facilitator will guide the IDIs, KIIs, and FGDs, and a note-taker will document non-verbal cues and main points. The note-taker will also take notes to ensure no loss of information in the event of a technological failure and to provide contextual information. For FGD and KII participants, basic demographic background information about each respondent (such as title/role, age, gender, and education level) will be audio-recorded at the start of the FGD or KII, but no responses will be traced to specific individuals during analysis and reporting. At the end of all completed IDIs, KIIs, and FGDs, study staff will review all recordings to ensure they are audible and all notes for legible handwriting. Ambiguous information from interviews or FGDs will be clarified with the source. As far as practical, the field team will transcribe audio-recordings, with support from other qualitative data analysts and coders. Interviewers/facilitators will read the transcripts for completeness and fill in gaps using their interview and field notes. Transcribed interviews will be stored in password-protected files.

Table 5. Summary of mixed methods data collection activities for completing Specific Objective #2.

Method	Activity Ty	Number	Total Particip	Approxir
				Time for
				activity

Structured Observa	Non-human s research	~2 observations—1 at each site included in the "mini" wedge trial	0 (Non-participat	1–2 hours
Costing survey	Non-human s	Reviewing administrative records with assistance of informants	0 (Non-participate	~1 hour
Focus group discussions	Research	~2 FGDs total— ~1 FGD with NPHW at each site	~8 – 16	~2 hours
	Research	~2 FGDs total with CHWs/lay health providers – ~1 FGD each site	~8 – 16	~2 hours
	Research	Brief implementation survey done with all FGD participants FGD	~16 – 32	~15 minute
In-depth interviews	Research	~20 total from among nested cohort participants— ~10 per	~20	~1 hour
Key informant interv	Research	~5 - 10 in each pilot site with key stakeholders	~10-20	~1 hour
WHOQOL-HIV-BRE survey	Research	~200 nested cohort participants (~100 per pilot site fron cohort)	~200	~30 minute:
Discrete Choice Ex (DCE) survey	Research	~200 nested cohort participants	~200	~30 minute

v. Study instruments, questionnaires, lab instruments, and analytic tests

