The primary measures for the pilot are adoption, acceptability, feasibility, appropriateness, as well as the preliminary effect of the TASKPEN intervention. We will assess implementation outcomes principally using a handful of theoretical frameworks. A brief questionnaire will be administered that will feature the simple 12-item implementation survey (incorporating empirically supported measures for acceptability, feasibility, and appropriateness) mentioned above, among other implementation-relevant items⁹⁸. We will further examine **acceptability** in our qualitative data as a construct comprising multiple dimensions⁹⁹. We will include open-ended questions guided by established implementation science frameworks such as the CFIR to elaborate on what makes the intervention appropriate or not and acceptable or not. We will further evaluate **feasibility** in our qualitative data by applying the theoretical basis of "compatibility" from Rogers' "Diffusion of Innovation" theory, among other theories¹⁰⁰.

We will describe implementation outcomes of **adoption** and **reach** according to RE-AIM. We will also calculate **retention** as the proportion of participants enrolled in the nested cohort and considered to be engaged in care at ~6 months. We will measure **adherence** in the nested cohort by reviewing pharmacy records at ~6 months to determine consistent access to anti-hypertensive, diabetes, and dyslipidaemia medications, as appropriate, as well as antiretroviral therapy. For the patient surveys, we will ask participants about adherence and review pharmacy records to examine medication adherence overall at the study sites.

Finally, we will pilot the feasibility, applicability, and completeness of the following measures in the cross-sectional assessments and nested cohort for adoption in the future follow-on trial:

- 1. **Dual** HIV and NCD disease control, defined as:
 - a. HIV RNA level of <200 copies per milliliter on the most recent measure; **AND**

- The absence of the following NCD conditions as defined by the nested cohort eligibility criteria:
 1) uncontrolled systolic hypertension;
 2) uncontrolled diabetes mellitus;
 and
 3) uncontrolled dyslipidaemia.
- 2. 10-year ASCVD risk score (based on American College of Cardiology/ American Heart Society guidelines)
- 3. The HIV-specific *D.A.D. CVD risk score*: (The Data-collection on Adverse Effects of Anti-HIV Drugs) score.
- 4. Quality of life as measured by WHOQOL-HIV-BREF ¹⁰¹.

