For qualitative data, final qualitative transcripts will be reviewed for accuracy against original notes and recordings, for at least 5% of the transcripts. Any errors will be corrected by the person who conducted the interview using good clinical practice (GCP) correction procedures. Monitoring visits will be conducted on an ad hoc basis to ensure that data collection is being done well. Any retraining will be done on-site on an as-needed basis, to ensure that collected data are of high quality.

iv. Data ownership, sharing and governance

All study data will be owned by the Zambia Ministry of Health (MOH) as the stewards of the national HIV program. As the owners of the data, the Zambia MOH will ultimately be responsible for oversight of all data governance issues. Qualitative data will not be shared due to the small sample size involved and the potential for deduction. All decisions regarding data dissemination, for example at the request of a journal at the time of publication, will be made by the Zambia MOH as the owners of the data.

g. Data analysis

i. Quantitative data analysis

We will summarize background characteristics (for participants and facility) by the intervention periods (control, intervention). The preliminary effect of the TASKPEN intervention will be estimated by comparisons of the percentage of participants in the patient surveys with dual HIV/NCD control during the control period and the intervention period. We will also calculate CVD risk score based on the ASCVD, D.A.D, or similar and compare this outcome between the control and intervention periods. Binary outcomes will be analysed using generalized linear mixed logistic model with margins to estimate risk ratio and risk difference adjusted for key potential confounders. Health facilities will be specified as random effects while time will be specified as fixed effect in the model. Continuous outcomes will be analysed using linear models to estimate mean score difference in an analogous way.

Quality of life score will be analysed in a similar way. P-values less than 0.05 will be considered statistically significant. We do not plan to impute missing values. All analyses will be performed using Stata 16 MP4 (StataCorp, College Station, TX, USA).

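### Quality of life is to be compared between control and intervention periods, but each cohort member is scored once at an unfixed visit, so separating the effect from site is left to chance

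*Combined protocol and SAP*

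**What the plan says.** All references are to section 8 of the combined protocol and SAP, under Specific Objective #2 unless stated.

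- **Role.** Specific Objective #1, part b.ii, describes the quality-of-life instrument as one "which will be a secondary outcome for the pilot and the later follow-on trial".
- **Collection.** Part e.iii gives cohort members the "WHOQOL-HIV-BREF-Zam instrument and the discrete choice experiment questionnaire one time each during one of their ~4 follow up visits". Part d.vii places those visits at about 2 weeks, 3, 6 and 9 months after the baseline survey.
- **Sample.** Part d.i plans "administration of the adapted WHOQOL-HIV-BREF-Zam and discrete choice experiment (DCE) questionnaire to these ~200 participants", and Table 5 agrees: "200 nested cohort participants (~100 per pilot site". Part e.vii is wider. It lists the instrument (item 4) among measures to be piloted "in the cross-sectional assessments and nested cohort for adoption in the future follow-on trial".
- **Other use.** Part e.iii also uses the score "to investigate the ability of the instrument items to discriminate between those with and without active symptoms".
- **Analysis.** Part g.i compares the control and intervention periods and states: "Health facilities will be specified as random effects while time will be specified as fixed effect in the model". It then adds: "Quality of life score will be analysed in a similar way". The next sentence sets 0.05 as the significance threshold.
- **Switch dates.** Parts b and e.iii put the first site's switch straight after the baseline survey and the second site's straight after the midline survey at about 3 months.

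**The concern.** A control-versus-intervention comparison in a two-site stepped wedge needs scores from both sites on both sides of a switch. Here each person contributes one score, so nobody has a before-and-after pair, and the visit is left open. Every eligible visit falls after the baseline survey, so site A may have no control-period score at all.

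A field team could follow the collection section exactly and still leave the analysis section nothing to estimate except a difference between two facilities, or leave it with no control data. A control-period score missed at site B cannot be recovered after B switches.

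The outcomes section adds a smaller inconsistency by naming the cross-sectional assessments as a source of quality-of-life data, when the sample descriptions give the instrument to the cohort only.

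**Working it through.** **The plan's own figure.** No sample size or power is stated for quality of life. The only stepped-wedge figure (part d.v) is for dual HIV/NCD control: 188 per site per survey, 0.75 versus 0.60, intraclass correlation (ICC) 0.25, two-sided 0.05, 80% power. It reproduces with the Hussey-Hughes variance. Let s = 0.75 × 0.24/188 = 0.000957 and τ² = 0.25 × 0.24 = 0.06. For 2 sites and 3 periods, the variance is 2s(s + 3τ²)/(s + 2τ²) = 2 × 0.000957 × 0.180957/0.120957 = 0.002865, so SE = 0.0535. Then 0.15/0.0535 − 1.96 = 0.84, which is 80.0% power. This does not carry over to quality of life, which has a different sample and schedule.

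**Exposure at each cohort visit.**

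| | ~2 weeks | ~3 months | ~6 months | ~9 months |
|---|---|---|---|---|
| Site A | TASKPEN* | TASKPEN | TASKPEN | TASKPEN |
| Site B | control | control | TASKPEN | TASKPEN |

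*Assumes A has switched by then. The visit is timed from each person's own survey and the length of the survey is not stated, so some of A's 2-week visits could precede the switch.

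**Can the effect be separated from site?** Take 100 scores per site, one per person, SD = 1, with site, visit and exposure as fixed terms. The estimate is (B after − B before) − (A after − A before), where before and after refer to B's switch. Its variance is the sum of 1/n over the four groups.

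| When scores are taken | Result (95% half-width) |
|---|---|
| Everyone at any single visit | not estimable apart from site |
| Only ~6 and/or ~9 months | no control scores |
| A at ~3, B at ~6 months | no control scores |
| A at ~6, B at ~3 months | not estimable |
| Half ~2 weeks, half ~3 months | not estimable; ±0.55 if A's 2-week visits precede its switch |
| 90% at ~3, 10% at ~6 months | variance 2/90 + 2/10 = 0.222, SE 0.471, ±0.92 |
| Half ~3, half ~6 months | variance 4/50 = 0.08, SE 0.283, ±0.55 |
| Even spread over four visits | variance 4/50 = 0.08, SE 0.283, ±0.55 (±0.64 if A's 2-week visits precede its switch) |

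**The plan's random-facility model.** If all scores are taken at ~3 months, exposure coincides with facility, and the estimate is entirely the between-site difference whatever the ICC.

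Under an even spread, treat the facility variance as known. The model then pools two contrasts. The within-site contrast has variance 0.08(1 − ICC). Twice the difference in site means has variance 4 × [2 ICC + 2(1 − ICC)/100]. The share of a constant site difference that enters the estimate is twice the weight on the second contrast: 66%, 28% and 6% for an assumed ICC of 0.01, 0.05 and 0.25. At ICC 0.01, for example, the variances are 0.0792 and 0.1592, the weight is 0.332, and doubling gives 66%. So dependence on the site difference is complete for a single visit, but partial and ICC-dependent for a spread.

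**Two scores per person, at ~3 and ~6 months.** Change at B minus change at A has SE = √[4(1 − ρ)/100], where ρ is the assumed within-person correlation. For ρ = 0.3, 0.5 and 0.7 the half-widths are ±0.33, ±0.28 and ±0.21.

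**Site-by-time variation.** None of these intervals includes it. With an assumed SD of 0.1 per site-visit, the variance rises by 4 × 0.01 = 0.04. The paired ±0.28 becomes 1.96 × √0.06 = ±0.48, and the single-score ±0.55 becomes 1.96 × √0.12 = ±0.68.

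**The case against.** The strongest reply is that little depends on this comparison. Parts b and d.v describe the cohort as a feasibility exercise without a pre-set hypothesis test, and part e.vii introduces the measure as one whose feasibility and completeness are being piloted. That stands and limits the consequence. It does not remove the planned analysis.

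A second reply is that one of about four visits reads as naturally as a spread, and under a spread the effect is estimable. That also stands. A reader might infer that the effect can never be separated from site; the documents support only that separation depends on timing the plan does not control.

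Other stronger readings are tempting but not supported:

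- **The estimate will drive the larger trial's design.** Part b takes the pilot effect size for planning from the survey data.
- **The reported interval will badly under-cover.** Any specific coverage figure needs all scores at ~3 months, a particular estimator and a quality-of-life ICC. The plan fixes none of these; its 0.25 is for dual control.
- **Table 4 shows the two tentative sites are not comparable.** As far as the broken table can be read, it concerns completeness of routine records such as blood pressure. It does not bear on quality-of-life means.
- **The 6-month medication possession ratio has the same fault.** No section says it is meant to show change at B's switch.

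The outcomes list can be read as covering two samples jointly, with not every measure taken in both. That makes the sample mismatch minor, but one sentence would settle it. The different sources for retention in parts e.vii and g.i are a separate wording point.

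**Conclusion.** The concern holds in a limited form. The collection and analysis sections do not fit together: one permitted way of collecting the score turns the planned comparison into a pure site difference, another leaves it without controls, and a third gives about ±0.55 SD. Which one occurs is left to chance.

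This rests on A switching just after the baseline survey and B after about 3 months, and on about 100 scores per site. If some of A's 2-week visits precede its switch, a mix of 2-week and 3-month visits becomes informative, but any single visit still is not. No primary measure is affected. It should be settled before the first cohort visits, because anyone scored at 2 weeks has used their one administration.

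**What to change.** Choose one, and make parts e.iii, e.vii and g.i agree with it.

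1. **Split the visit.** Keep one administration. Randomly assign half of each site's cohort to ~3 months, before B's switch, and half to ~6 months. Precision is about ±0.55 SD. Cost: an allocation list and a protocol amendment; no extra interviews.
2. **Score everyone twice**, at ~3 and ~6 months, and report change at B minus change at A. Precision is ±0.21 to ±0.33 SD for an assumed within-person correlation of 0.7 to 0.3. Cost: 200 × about 30 minutes = about 100 extra interview hours at visits already scheduled, more respondent burden, and an amendment.
3. **Fix one visit for everyone**, keep the known-group use, and delete the quality-of-life comparison from part g.i. Cost: wording only, but the pilot then gives no quality-of-life effect estimate.

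Under 1 or 2, report an estimate with its interval and no significance test. State three limits: only B's switch is observed; A is a clean comparator only if the effect does not grow with exposure; and with two sites the interval omits site-by-time variation and is therefore too narrow.

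Under any option, limit item 4 of the outcomes list to the cohort, to match parts d.i and e.iii and Table 5. Adding the instrument to all surveys instead would take about 1128 × 0.5 h = 564 hours.

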site, both pilot sites A and B will implement the full TASKPEN intervention for another ~3 months after which time a third and final "end line" patient survey will be conducted. Survey data will be used to estimate the pilot effect size of the TASKPEN intervention to aid in planning a future larger trial and to measure WHO PEN process indicators for all PLHIV in care who accessed routine health services during the pilot period.

Complementing the baseline, midline, and endline patient surveys will be a "nested cohort" of PLHIV with cardio-metabolic comorbidities enrolled at both sites beginning at baseline. At each site, we will enrol a subset of ~100 baseline survey participants (i.e., ~200 total) found to have at least one cardio-metabolic complication or risk factor (see below) on the baseline survey. We will then follow these nested cohort participants longitudinally for ~9 months at site A and site B. A nested cohort sample size

TASKPEN Study

of 200 PLHIV was selected to represent about 50% of all baseline survey participants who are estimated to have a cardiometabolic co-morbidity at each site (i.e., ~188 PLHIV in care per site who complete a baseline survey x ~50% of survey participants with hypertension, diabetes, and/or dyslipidaemia = ~100 participants per site), consistent with estimates for the prevalence of cardiometabolic comorbidities among PLHIV in Lusaka, Zambia. Moreover, the nested cohort sample size of ~200 total participants (~100 per site) is intended to assess the feasibility of the intervention and longitudinal follow up of study participants to inform a future larger trial; it is not intended to test a hypothesis *a priori*. By enrolling a nested cohort, we can use their data to enrich inferences made from the cross-sectional surveys and will be able to make more granular comparisons between and within sites (i.e. with an external and internal comparator group, respectively).

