For the cross-sectional patient surveys, we will survey a consecutive sample of 188 eligible patients in care at each clinic at each of the 3-time points (i.e., baseline, midline, and end-line) using a stepped-wedge cluster-randomized design. Applying this design with a sample of 2 clusters (i.e., sites), 3 survey time points, 2 steps, 1 cluster switching from control to intervention at each step, and an average of 564 subjects per cluster (i.e., 188 participants per cluster per period) achieves 80% power to detect a risk ratio of 1.25 (for the risk of dual HIV/NCD control during the intervention period compared to the control period) at the 0.05 significance level with an inter-class correlation coefficient of 0.25. We assumed that

the proportion of participants achieving dual HIV/NCD control is 0.75 under the alternative hypothesis, and 0.6 under the null hypothesis, and used the two-sided Wald Z-Test as the test statistic. Based on the above calculation, we will survey 564 eligible patients at each clinic across the 3-time points (i.e., 3*188=564 eligible patients) to achieve **a total sample size of 1128 participants** for the mini stepped-wedge. It is important to note that participants previously surveyed will not be eligible for subsequent surveys—i.e., once interviewed, a patient should not be eligible for interview in subsequent surveys unless they are part of the nestd cohort. Finally, as part of the baseline, midline, and endline cross-sectional surveys, we will review de-identified routine data for all PLHIV in care at the study sites during the study period to estimate HIV viral load completeness, NCD-variable data completeness (e.g., routine weight and blood pressure measurements), and performance on WHO PEN indicators in the routine medical record.

For the nested cohort component, the total sample size of ~200 participants was selected for operational feasibility and to assess our ability to collect longitudinal cardio-metabolic data, but does not involve *a priori* hypothesis testing.

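### Non-significance at p<0.05 is the only stated ground for considering WHOQOL-HIV-BREF-Zam items for removal, in a cohort of about 200 that was not sized for testing

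*Combined protocol and SAP*

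**What the plan says.** Under Specific Objective #2, the section on quantitative research data collection gives the WHOQOL-HIV-BREF-Zam to the nested cohort to see whether its items separate "those with and without active symptoms related to HIV and co-morbid NCDs", "as determined by differences in mean scores". The decision rule follows: "A p-value less than 0.05 will be considered significant", and "items with non-significant differences between the two groups may be removed from a future iteration of the instrument". The test is not named, and neither its sidedness nor the expected group sizes are given.

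Three other statements bear on this:

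- **Cohort size.** The study design section says of the cohort that "it is not intended to test a hypothesis" a priori. The sample size section adds that "the total sample size of ~200 participants was selected for operational feasibility".
- **Responses per item.** Each participant completes the instrument "one time each during one of their ~4 follow up visits", so an item has at most about 200 responses.
- **Use of the instrument.** Under Specific Objective #1, preparation of data collection tools, quality of life is described as a measure "which will be a secondary outcome for the pilot and the later follow-on trial". The same section has translators and investigators settle unclear items by consensus. That is a review of wording and sets no criterion for dropping an item.

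**The concern.** A p-value of 0.05 or more does not show that an item fails to discriminate. It may mean that the difference is absent, or that it is real but too small for this sample to detect. The plan offers nothing to tell these apart: no smallest difference of interest, no expected split by symptoms, no power and no second criterion. It attaches a consequence to an item-level significance test in a cohort that it elsewhere says was not designed for testing.

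Two features could make the test weaker than the total of about 200 suggests. The symptom groups are not sampled to a target, and imbalance lowers power. Every cohort member also has at least one cardio-metabolic condition or risk factor, so both groups come from an affected population and small differences are plausible.

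At stake is the content of a later version of an instrument that this work prepares for the follow-on trial. A useful item could become a candidate for removal through lack of precision.

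**Working it through.** The plan states no power, effect size, SD or split for this comparison, so it has no figure of its own to reproduce. The check asks how often an item with a real difference would miss p<0.05.

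**Inputs from the documents:** total about 200; threshold 0.05; comparison of two group means; one administration per participant.

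**Assumptions:** two-sided test; true standardised difference d of 0.2 to 0.8 (SD = 1); splits from 100:100 to 20:180. Clustering by the two sites and the ordinal item scale are not modelled.

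**Formulae:** SE = √(1/n₁ + 1/n₂). Power ≈ Φ(d/SE − 1.960). Chance of missing = 1 − power. The opposite tail is negligible at the values worked through below.

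**Worked for d = 0.3:**

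- 100:100. SE = √(0.01 + 0.01) = 0.1414; d/SE = 2.121; power = Φ(0.161) = 0.564; missed 43.6%.
- 50:150. SE = √(0.02 + 0.00667) = 0.1633; d/SE = 1.837; power = Φ(−0.123) = 0.451; missed 54.9%.

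**Worked for d = 0.5:**

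- 100:100. d/SE = 3.536; power = Φ(1.576) = 0.942; missed 5.8%.
- 50:150. d/SE = 3.062; power = Φ(1.102) = 0.865; missed 13.5%.

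**Chance that a truly discriminating item is non-significant, total 200:**

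| Split | d = 0.2 | d = 0.3 | d = 0.4 | d = 0.5 | d = 0.8 |
|---|---|---|---|---|---|
| 100:100 | 70.7% | 43.6% | 19.3% | 5.8% | <0.1% |
| 60:140 | 74.7% | 50.6% | 26.4% | 10.0% | 0.1% |
| 50:150 | 76.9% | 54.9% | 31.2% | 13.5% | 0.2% |
| 20:180 | 86.7% | 75.4% | 60.4% | 43.6% | 7.6% |

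The noncentral t distribution gives power within 0.006 of these values.

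**Fewer evaluable responses.** If only 160 were evaluable (assumed), d = 0.3 would be missed 52.5% of the time at 80:80 and 62.4% at 40:120.

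**What the cohort can detect.** The difference detectable with 80% power is (1.960 + 0.842) × SE. This is 0.396 SD at 100:100, 0.457 at 50:150 and 0.660 at 20:180. To detect 0.3 SD with 80% power in equal groups needs 2 × (2.802)² / 0.3² ≈ 174.5, so 175 per group or 350 in all.

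**The case against.** The strongest reply is that the sentence is permissive and looks ahead. Items may be removed, and only from a later version. Pilot scoring is untouched, no primary measure of the pilot depends on it, and revising a tool before a larger trial is what a formative study is for. All of this stands, and it is why the point is minor. It does not rescue the criterion: with no other ground stated, the p-value alone decides which items come up for removal.

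A second reply is that known-group comparisons contrast groups expected to differ, so 0.3 SD may be too small a benchmark. At 0.5 SD, power is 94% at 100:100 and 86% at 50:150. This also stands in part. The documents do not say how large the differences should be, so it cannot be claimed that a non-significant result here mainly reflects low power.

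A reader might infer two stronger things that the documents do not support:

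- **That about half of the useful items would be dropped at this sample size.** Half is not a property of 200 participants. It needs a true difference of about 0.28 to 0.32 SD and a split between 50:50 and 25:75. Over the range in the table the chance runs from under 0.1% to about 87%. It is also the chance of becoming a candidate, not of being removed.
- **That removal would break a planned comparison of scores between the pilot and the follow-on trial.** Quality of life is to be measured in both, but no such comparison is described. The data analysis section compares control and intervention periods within the pilot.

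**Conclusion.** The point holds as a minor one. The plan makes non-significance the sole stated trigger for considering an item for removal, in a cohort that it says was not sized for testing and with an uncontrolled split by symptoms. Under a two-sided test at 0.05 with 200 responses, and splits from 100:100 to 50:150, a truly discriminating item would become a candidate about 44% to 55% of the time if the true difference is 0.3 SD, and about 6% to 14% if it is 0.5 SD. The effect sizes and splits are assumptions. A more uneven split or missing responses would raise these figures, and larger true differences would make them small.

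**What to change.** Delete the p-value criterion for item removal. In its place:

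1. Report each item's standardised difference between the symptom groups with its 95% interval, and the number in each group.
2. State that non-significance alone is not a ground for removal.
3. Base any later revision on the size and precision of the difference together with other item evidence, for example missingness, item-total correlation and the semantic review already planned.

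A mechanical cut-off based on the interval, such as flagging items whose upper 95% limit lies below 0.3 SD, would not be a good substitute. The half-width (1.960 × SE) is 0.277 SD at 100:100, 0.320 at 50:150 and 0.388 at 30:170. An item would be flagged only if its estimate fell below 0.3 minus the half-width, that is below 0.023, −0.020 or −0.088 SD. An item with no discrimination at all would then escape about 44%, 55% and 67% of the time. Judgement on several kinds of evidence suits this sample better.

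The cost is one table and some wording, with no added data collection. Fewer items would be removed.
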